##### *14.1.2 Assessments performed in discrete locations*

All study activities will be performed in discrete locations at URMC. In-person consent will be performed in a private room, usually where their oncology appointments typically take place (e.g., Wilmot Cancer Institute, Pluta Cancer Center). Blood draws will be performed in clinic locations where blood is typically drawn.

##### *14.2 Study teams' access to participant information*

eRecord will be used to help screen patients and extract data. Only those with proper training will have access to this database and medical records.

Some study data will be collected electronically using REDCap software, and any eConsents will be conducted using REDCap. REDCap is a secure, web-based application for building and managing online surveys and databases and is made available through the CTSI. Study data in REDCap will only be accessed by members of the study team.

All other study data—paper-and-pencil forms, biological samples—will be labeled with Participant ID and participant initials and not identifiable information. Only members of the study team or those analyzing the data/samples will have access to these.

All data will be compiled into several databases that will identify participants by Participant ID and *not* name or contact information. If data are shared in the future with other researchers (e.g., a trainee), only

databases without identifiable information will be shared and access will only be given to that specific individual.

#### *14.3 Contacting participants*

This is an 8-week study, and participants will be contacted throughout the study period. We will check in with participants approximately weekly to assess adverse events and ask how they are doing. We will also schedule appointments and remind participants of appointments. For these contacts, we will ask if phone, text, or email is preferred. REDCap software also contacts participants with reminders to complete questionnaires.

#### *14.4 Data confidentiality, storage, and sharing*

Paper-based data will be stored in a locked cabinet in [name] office in the Cancer Control division of URMC in Saunders Research Building. Electronic data will be stored on [name] desktop computer in her office in Saunders research building. The Cancer Control Unit is an office suite secured by electronic key cards; [name] personal office is secured by a traditional key; [name] file cabinet is secured by a unique traditional key; and [name] computer is password-protected. Electronic research records are stored on URMC's password-secured and firewall-protected networks. These are the same methods of security used for patient medical records. Biological samples will be stored in the CCPL (Director: [name], co-investigator). In the rare case that any data are transferred outside of the University, only deidentified databases will be shared with approved individuals for private access. Databases will be transferred through URMC's HIPAA-compliant box.com under the direction of [name] or a designee, with oversight by the Cancer Control Information Technology staff. We anticipate that data will only be shared for research purposes only, but it is possible that data could be used for teaching or other purposes. To reiterate, all shared data will be deidentified.

Only members of the study team will have access to the stored data, and only members of the study team and CCPL will have access to the stored biological samples. All individuals who have access to the data will need to complete human subject training as required by URMC. Participants' individual research records will not be shared with their treating physician, unless they provide consent or the subject's treating physician is a study physician, in which case they will have access to study data as a study co-investigator. Overall study results may be presented to participants, faculty, and staff at URMC after completion of the study. Study results will be presented at local meetings and seminars and professional meetings, published, and reported on clinicaltrials.gov.

All study data will be kept for at least six years after the study and all reports and publications are complete.

### **15. Data/sample storage for future use**

All data (information and human blood samples) collected for the current study will be used in post-hoc analyses as appropriate. These analyses could provide preliminary data for future studies. Blood samples will be stored and data will be used for future studies only with prior consent of subjects. The consent form contains appropriate language related to banking and subjects are given the option to have their samples stored or to have them destroyed following analysis of the study hypotheses. Long-term data and sample storage will be in the same locations as described in §14.4.

Any individual who would like access to deidentified raw data or samples must submit a request to the study chair (i.e., [name]) via a written request (e.g., email). If [name] considers the project

appropriate, she will approve a release of the data or samples and transfer the data/samples in a safe, HIPAA-compliant manner as described in §14.4.

## 16. Data analysis and monitoring

### 16.1 Adverse event reporting

An **adverse event** is any symptom, sign, illness, or experience that develops or worsens during the study, whether or not the event is considered related to the intervention. To assess the severity of adverse events, we will use the CTCAE, version 5, recommended by the NCI. The CTCAE displays Grades 1 through 5 with unique clinical descriptions of severity for each adverse event based on this general guideline:

- **Grade 1:** Mild; asymptomatic or mild symptoms; clinical or diagnostic observations only; intervention not indicated.
- **Grade 2:** Moderate; minimal, local or noninvasive intervention indicated; limiting age-appropriate instrumental activities of daily living.
- **Grade 3:** Severe or medically significant but not immediately life-threatening; hospitalization or prolongation of hospitalization indicated; disabling; limiting self-care activities of daily living.
- **Grade 4:** Life-threatening consequences; urgent intervention indicated.
- **Grade 5:** Death related to adverse event.

A **serious adverse event** is any adverse medical experience that results in death, or is life-threatening, or requires inpatient hospitalization of at least 24 hours, or prolongs existing hospitalization, or results in persistent or significant disability/incapacity, or causes a congenital anomaly/birth defect, or requires medical or surgical intervention to prevent permanent impairment or damage.

Each adverse event will be evaluated in regard to whether the adverse event was potentially a consequence of the intervention. Attribution will be categorized into one of five categories (**Table 5**). The subject's referring oncologist, designee, or study medical monitor will determine the grade and attribution.

Attribution	Description
Unrelated	The adverse event is clearly NOT related to the intervention
Unlikely	The adverse event is doubtfully related to study intervention
Possible	The adverse event may be related to study intervention
Probable	The adverse event is likely related to study intervention
Definite	The adverse event is clearly related to study intervention

**Table 5.** An assessment of the relationship between the adverse event and the study intervention will be categorical.

With that information, **we will only report the following events:**

- Serious, related, and unexpected events will be reported to the Data Safety Monitoring Committee and the RSRB in an expedited manner.
- Grade 4 or 5 events regardless of attribution will be reported to the RSRB at each continuing review.

We are paying close attention to weight loss and gastrointestinal distress, so we will closely monitor these symptoms but only report them to the RSRB if they fit the description above.

## 16.2 The Data Safety Monitoring Committee

The James P. Wilmot Cancer Institute Data Safety Monitoring Committee (DSMC) will serve as the DSMC of record for this study. The DSMC provides oversight of study progress and safety by review of accrual and events at regularly scheduled meetings. The frequency of review is determined by the size, risk, and complexity of the trial.

[name], the study chair, will conduct continuous review of data and subject safety. The Investigator will submit annual progress reports according to the timing set by the DSMC for review. The review will include the number of subjects enrolled, withdrawals, and serious adverse events (both expected and unexpected). A copy of the Adverse Event spreadsheet along with the Progress Report will be submitted to the DSMC for review. Actual review dates will be assigned when the first participant is accrued.

Any serious adverse event that is serious, related, and unexpected will be reported within 10 calendar days to both the Safety Coordinator (e.g., [name]) and the RSRB. The DSMC Chair will determine whether further action is required, and when subject safety is of concern. When subject safety is of concern, an interim meeting may be called.

[figure not shown]
Serious adverse events that are related and expected or unrelated and unexpected will be reported to the Committee for review at the quarterly meeting. Serious adverse event reports will include sufficient detail so that the DSMC can determine the severity, toxicity grade, expectedness, treatment required, and a follow-up report documenting resolution of if there are sequelae. Serious adverse events that require detailed reports (but not necessarily expedited) are expected, related, non-hematologic toxicities of grade 3, 4 or 5.

## 17. Data analysis plan

### 17.1 Sample size determination

This is a two-arm randomized controlled trial that will assess feasibility of delivering a Mediterranean Diet intervention to patients undergoing chemotherapy, as well as the preliminary efficacy of a Mediterranean Diet intervention vs. usual care on the prevention of cancer-related fatigue. Our sample size is based on our fatigue outcome as measured using the FACIT-F fatigue subscale, which is a 13-item scale with responses that range from 0-4; the FACIT-F subscale score ranges from 0-52 and a higher score indicates greater wellbeing and less fatigue. The minimal clinically important difference for the FACIT-F is 3 points.

We plan to recruit a total of 42 participants and randomize them in a 2:1 ratio, intervention: control (28:14) using computer-generated block randomization with blocks of 3 or 6. Patients will be stratified based on how frequently their chemotherapy is planned to be administered. One strata will include patients who plan to receive weekly, biweekly (Q2w), or every 4-week (Q4w) regimens, and the other strata will include those on other regimens (e.g., Q3w). Thus, those in the first strata will complete 4-week and 8-week assessments for our study at the end of a chemotherapy cycle, while those in the second strata will be completing assessments in the middle of their cycle. (If there are

**Fig. 3.** Effect size vs. sample size at 70% and 80% power with 33 participants on the study.

dose delays or changes to the chemotherapy schedule, we will still collect assessments at the originally planned time.) We estimate attrition between approximately 20 and 25%, thus we estimate to retain 33 (22:11) evaluable patients. This sample size is appropriate for small randomized pilot studies and it will allow us to obtain preliminary estimates of descriptive statistics [mean, standard deviation (SD), and confidence intervals (CI)]. The primary endpoint is the change in fatigue as measured by FACIT-F from baseline (T1) to 4 weeks (T2). Assuming a correlation of 0.50 between T1 and T2 FACIT-F measurements, a total sample size of n=33 will provide 80% power at the 0.15 two-sided significance level to detect an effect size (ES, standardized mean between-group difference) of 0.75 of the intervention effect on change in T2-T1 FACIT-F using analysis of covariance (ANCOVA) with T1 FACIT-F as a covariate (**Fig. 3**). The estimates of T1-T2 correlation and attrition rate are based on our prior studies.

Feasibility is often determined for nutrition interventions among 10-15 participants (e.g.,); pilot preliminary efficacy studies usually recruit 20-30 (e.g.,). **Table 6** below shows prior studies that are similar to this one, including their sample size.

Study	n	Population	Intervention	Outcome	Results
Zick et al. (2017) 	30	breast cancer survivors	Fatigue reduction diet vs. General Health Curriculum (time and attention control) for 3 months	Brief Fatigue Inventory	From baseline to 3-months, fatigue improved by 44±39% in diet group compared to 8±34% in the control group (p=0.01)
Skouroliakou et al. (2018) 	70	breast cancer survivors	Mediterranean Diet for 6 months vs. handout	serum antioxidant capacity and body composition	The dietary intervention based on Mediterranean Diet improved serum antioxidant capacity, body composition, and glycemic profile.
McMillan et al. (2011) 	27	healthy women in their 20's	Mediterranean Diet vs. control for 10 days	Profile of Mood States	A group × time interaction demonstrated that the Mediterranean Diet reduced fatigue (p=0.16) and improved vigor (p<0.01).
Okumatsu et al. (2017 and 2019) 	32	female breast cancer patients on endocrine therapy (after adjuvant treatment)	1200 kcal/day diet + exercise vs. control	cancer-related fatigue (exact measure not stated)	Fatigue decreased 39% in the intervention group and was stable in the control group.
Lee et al. (2015) 	24	young, healthy women	Mediterranean Diet vs. habitual diet for 10 days (cross-over)	mood, cognition, and cardiovascular measures	Improvements in mood (contentment, alertness, confusion), cognition (memory recall), and cardiovascular function (augmentation pressure) were observed with the Mediterranean Diet.
Djuric et al. (2011) 	40	breast cancer patients beginning chemotherapy	Nutrition and diet intervention for 12 months	body weight and body composition	Body fat percentage increased in the control arm and decreased in the intervention arm

**Table 6.** Prior studies that are similar to this one, including sample size.

### *17.2 Data Handling, Rigor, Quality, and Reproducibility:*

Data will be entered in REDCap electronic forms and electronically collated in a HIPAA-compliant REDCap database managed by our Division. After collation, data will be audited electronically and visually, as needed, for errors. Appropriate graphical or statistical diagnostics methods will be employed in each of the analyses to evaluate distribution of variables (e.g., to identify shape of the distribution and outliers) and also to evaluate the model assumptions (e.g., if deviation from the statistical assumptions is found, we will use alternative methods such as transformations or nonparametric analyses). Outliers that are detected will be investigated to determine if they are due to error. If not, analyses will be conducted with and without them to assess sensitivity. Because this is a preliminary efficacy study, unless stated otherwise, all hypothesis testing will be at the two-sided 0.15 level as appropriate for screening trials. SAS, JMP, and/or R software will be used for the analyses. Following the intent-to-treat principle, all randomized survivors will be analyzed in the arm as allocated, regardless of their compliance with the intervention or Mediterranean Diet contamination in the control group.

Although participants will be randomly assigned, differences may be present between study arms on demographic or clinical variables. Study arms will be compared on baseline demographic (e.g., age), clinical (e.g., cancer diagnosis, type of chemotherapy), and behavioral (e.g., physical activity, smoking) variables. If significant imbalance is found for a variable, it will be included as a covariate in subsequent analyses following standard practice.

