#### *17.4.2 Aim 2: Patient-reported fatigue*

To provide estimates of efficacy comparing the Mediterranean Diet to usual care for alleviating fatigue, we will evaluate between-arm difference in mean change in FACIT-F fatigue subscale score from baseline to 4 weeks in an ANCOVA model. The outcome will be FACIT-F fatigue score at 4 weeks with arm included as a fixed effect and FACIT-F fatigue score at baseline as a covariate. To assess the moderating effect of the baseline level of fatigue we will test arm×baseline interaction. To further evaluate the longitudinal trajectory of fatigue and the maintaining effect of the intervention, we will incorporate FACIT-F fatigue score measured at all time points (T1, T2, T3) in a repeated measures linear mixed model. The impact of patient's variables (e.g., age, gender, body mass index) on the results will be assessed by adding the covariates to the models. The results of the analyses together with the estimates of distribution parameters (e.g., mean, SD) of T1-T3 FACIT-F fatigue score values as well as the change scores will be used in planning a future randomized trial.

We expect all measures of cancer-related fatigue to increase over the course of chemotherapy, though we hypothesize that the differences will be attenuated in the intervention group. We will also compare our baseline-to-post-intervention change scores to those obtained via historical controls (e.g., [name] et al., 2018).

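### At 2:1 allocation the primary ANCOVA keeps its 0.15 error rate only if the arms have similar spread, and the remedies named in 17.2 do not in general correct a difference

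*Combined protocol and SAP*

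**What the plan says.** Section 17.1 randomises 42 patients 2:1 (28:14) and expects 33 evaluable (22:11). It states that "a total sample size of n=33 will provide 80% power at the 0.15 two-sided significance level". The target difference behind that figure is an "effect size (ES, standardized mean between-group difference) of 0.75", and the calculation takes a correlation "of 0.50 between T1 and T2 FACIT-F measurements".

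Section 17.4.2 gives the Aim 2 model: "The outcome will be FACIT-F fatigue score at 4 weeks with arm included as a fixed effect", with baseline score as covariate. No robust standard error, Welch-type test or arm-specific variance is named there or elsewhere. That the residual variance is pooled over arms is inferred from this standard description; the plan does not use the term.

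Section 17.2 sets the level: "all hypothesis testing will be at the two-sided 0.15 level". It provides for diagnostics in each analysis and then: "if deviation from the statistical assumptions is found, we will use alternative methods such as transformations" or nonparametric analyses. The references cited for the nonparametric option are rank procedures.

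The benchmark for the size of an effect is in FACIT-F points (17.1): "The minimal clinically important difference for the FACIT-F is 3 points". Sections 17.4.3 and 17.4.4 carry similar models to the biomarkers and the other patient-reported outcomes.

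**The concern.** A pooled residual variance is weighted towards the larger arm. With arms of equal size this does little harm when the arms differ in spread. At 2:1 the standard error of the arm effect is too small if the smaller arm is the more variable, and too large if it is the less variable.

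The pilot's estimates and intervals are meant to feed the design of a larger trial, so an interval of the wrong width would carry into that design. The 0.15 screening level is already permissive, and it could move up or down unnoticed. If the response to an assumption failure is a transformed or rank analysis, the adjusted effect is no longer in FACIT-F points and cannot be set directly against 3 points.

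**Working it through.** **Inputs from the documents:** 22:11 evaluable, two-sided alpha 0.15, correlation 0.50, effect size 0.75 (17.1, 17.2). **Assumption:** the ratio of residual SDs between arms, which the documents do not give. It is varied from 1.15 to 2 in each direction.

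**1. The plan's own figure.** The residual SD after adjusting for baseline is √(1 − 0.50²) = 0.866. The standardised difference is 0.75/0.866 = 0.866, and the standard-error factor is √(1/22 + 1/11) = 0.369. Then 0.866/0.369 = 2.345, and Φ(2.345 − 1.440) = 81.7%. The noncentral t version with 30 df gives 80.6%. The stated 80% is reproduced under equal variances and is not in dispute.

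**2. Pooled against true standard error.** Leaving the covariate aside:

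- pooled variance of the difference = [(21·s₁² + 10·s₀²)/31]·(1/22 + 1/11)
- true variance of the difference = s₁²/22 + s₀²/11

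with s₁ the diet SD and s₀ the usual-care SD. Examples:

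- s₁ = 1, s₀ = 1.5: pooled 1.403 × 0.1364 = 0.1913; true 0.2500; SE ratio √(0.1913/0.2500) = 0.875.
- s₁ = 1, s₀ = 1.15: pooled 1.104 × 0.1364 = 0.1505; true 0.1657; SE ratio 0.953. The effective critical value is 1.477 × 0.953 = 1.408, which on t(30) is an error of about 17%.
- s₁ = 1.15, s₀ = 1: pooled 1.2185 × 0.1364 = 0.1662; true 0.1510; SE ratio 1.049. The effective critical value is 1.550, an error of about 13%.

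**3. Simulation of the full ANCOVA** (40,000 trials per row, normal data, no true effect, nominal 15%):

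| More variable arm | SD ratio | Pooled ANCOVA | Rank ANCOVA | HC2, Satterthwaite df |
|---|---|---|---|---|
| Neither | 1 | 15.1% | 15.1% | 15.1% |
| Usual care | 1.25 | 18.0% | 16.8% | 15.3% |
| Usual care | 1.5 | 20.4% | 18.7% | 15.2% |
| Usual care | 2 | 24.0% | 21.2% | 15.2% |
| Diet | 1.25 | 12.5% | 13.4% | 15.1% |
| Diet | 1.5 | 10.5% | 12.3% | 14.8% |
| Diet | 2 | 8.3% | 11.4% | 14.8% |

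A nominal 85% interval covers 100% minus the error, so about 82%, 80% and 76% in the three usual-care rows.

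**4. Is the allocation the cause?** At 17:16, pooled ANCOVA stays at 14.9-16.0% for ratios of 1.5 and 2 in either direction. The distortion comes from the 2:1 split.

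**5. Do transformations help?** With scores of assumed mean 30 and SD 10 points and usual care 1.5 times as variable, the error is 24.6% (log), 21.8% (square root) and 20.5% (square), against 20.4% untransformed. Where spread rises with the mean (a lognormal case), the log analysis runs at 14.8%, but its effect is a ratio.

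**6. Cost of the robust analysis.** With equal SDs, power is 79.9% pooled and 79.3% with HC2 and Satterthwaite df. With usual care 1.5 times as variable the figures are 66.5% and 58.9%, but there the pooled test is running at 20.4% error. With the diet arm 1.5 times as variable they are 60.3% and 67.3%.

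**The case against.** The case for leaving the plan alone has several sound parts.

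- **The ratio is assumed.** The only arm-specific fatigue spreads in the documents are in Table 6, for a fatigue-reduction diet pilot: 44±39% against 8±34%. If these are SDs, the ratio is 39/34 = 1.15 with the diet arm more variable, which gives about 13% error. That is mildly conservative. The scale and population differ, so it is only indicative, but it does not support ratios of 1.5 to 2.
- **The plan does not predict unequal spread.** A reader might infer that it does, from the expected attenuation of fatigue, the variable dietary intake or the arm-by-baseline test. The first concerns means, the second concerns diet rather than fatigue, and the third is a planned check.
- **The list in 17.2 is open.** A reader might infer that robust errors are ruled out. They are allowed, but not named.
- **Diagnostics may be graphical.** A median-centred Levene test at 0.15 detects a 1.5-fold ratio only about 39% of the time, but the plan does not commit to that test.
- **Point-scale figures remain.** Section 17.4.2 reports means and SDs of scores and change scores whatever model is used. The 3-point benchmark appears only in 17.1.
- **This is a feasibility pilot.** No stated decision rule turns on a shift of about 2 percentage points in error.

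All of this limits the weight of the point. It does not supply an adjusted arm difference in points with an interval that holds under unequal spread.

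**Conclusion.** The point stands as a conditional one. At 22:11 the ANCOVA's 0.15 level and interval coverage depend on similar residual spread in the arms. For ratios of 1.15 to 1.5, actual error is about 17-21% if usual care is more variable and about 13-10.5% if the diet arm is. At a ratio of 2 it is 24% or 8%. These figures assume normal residuals, correlation 0.50 and the expected retention. Without FACIT-F SDs by arm, neither the size nor the direction can be known in advance.

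Two stronger readings are tempting and are not supported. One is that the 0.15 level and the intervals simply fail: under equal spread they hold (15.1%). The other is that the remedies in 17.2 never work: ranks reduce the distortion, and a log transformation corrects it when spread rises with the mean. What can be said is that they do not in general correct it, and that they move the adjusted effect off the FACIT-F scale. This is a cheap improvement to a pilot plan, not a flaw that undermines it.

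**What to change.** In 17.4.2, with a matching line in 17.2, state that the ANCOVA arm difference will be reported in FACIT-F points with HC2 standard errors and small-sample Welch-type (Satterthwaite) degrees of freedom from the outset, not after a diagnostic. Apply the same to the parallel ANCOVAs for the other patient-reported outcomes and the biomarkers. Keep transformed and rank analyses as sensitivity analyses.

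The degrees of freedom should be named, because HC2 referred to t(30) runs up to about 17% when usual care is much more variable. The cost is a sentence or two in the plan, a change to the analysis code, and under about 1 percentage point of power when variances are equal.

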#### 4.2 Subject population

We will recruit 42 patients with cancer undergoing chemotherapy from Wilmot Cancer Institute or a satellite clinic (e.g., Pluta Cancer Center). In particular, these patients will have a recent diagnosis of cancer (any type except brain cancer), and will represent a broad range of patients seen at Wilmot Cancer Institute including young and old; men and women; those of various ethnic and racial categories (**Table 1**); those who are underweight, normal weight, and overweight; those with and without underlying metabolic dysfunction (e.g., diabetes); and those undergoing various types of chemotherapy treatment.

From previous local studies completed by our group, we expect a 20% withdrawal rate, resulting in approximately 33 participants with evaluable data (approximately 22 in the intervention group and 11 in the usual care group).

No vulnerable classes of subjects such as fetuses, neonates, children, pregnant women, prisoners, institutionalized individuals, or decisionally impaired adults will be recruited.

Total planned enrollment: 42 participants

**Table 1.** Targeted/planned enrollment by ethnic and racial categories:

Ethnic Category	Sex/Gender		
	Females	Males	Total
Hispanic or Latino	2	1	3
Not Hispanic or Latino	26	13	39
Ethnic Category: Total of All Subjects	28	14	42
Racial Categories			
American Indian/Alaska Native	0	0	0
Asian	2	1	3
Native Hawaiian or Other Pacific Islander	0	1	1
Black or African American	3	2	5
White	23	10	33
Racial Categories: Total of All Subjects	28	14	42

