#### 4.4.4 Exploratory aims and other symptoms and clinical factors

In order to assess the variation in fatigue over the course of a chemotherapy cycle, we will assess average fatigue at the end of each day using a single-item question on a daily diary.

To obtain more precise estimates on the effects of the Mediterranean Diet on cancer-related fatigue and metabolism we will account for several behavioral and clinical factors. For example, several patient-reported outcomes tend to be associated with fatigue (e.g., depression) and we will adjust for these potential factors in our analyses.

1. Aerobics Center Longitudinal Study (ACLS) physical activity questionnaire: The ACLS captures current physical activity and exercise, including walking, climbing stairs, and weight training. We will use this questionnaire to estimate the energy that each participant expends per week on physical activity.
2. Symptom Inventory (SI): The symptom inventory (modified from the MD Anderson Symptom Inventory) includes 19 items that are common in the cancer experience (e.g., pain, distress, lack of appetite, numbness and tingling, fatigue), as well as 8 items related to how much these symptoms interfere with activities of daily living and quality of life. As many symptoms often correlate with each other including fatigue (i.e., symptom clustering), it is important to capture the change in many symptoms from baseline to post-intervention. Exploratory analyses will probe whether adherence to the diet or high consumption of any dietary component correlates with the change in any of these symptoms over time.
3. Brief Fatigue Inventory (BFI): The BFI is a 10-item fatigue questionnaire that is also validated and commonly used. It captures fatigue *now* as well as the usual and worst in the last 24 h. It also includes 6 single-item questions regarding how fatigue has interfered with general activity, mood, work, etc.
4. FACT-Cog: The FACT-Cog is a 41-item questionnaire designed to assess cognitive challenges identified by patients with cancer.
5. Brief Pain Inventory: The Brief Pain Inventory (BPI)-Short Form is a 15-item questionnaire designed to assess the severity of pain and its impact on functioning.

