#### *8.2.2 Source of record or measures*

The Clinical Record contains weight, height, current menopausal status, Karnofsky Performance Status (KPS) or Eastern Cooperative Oncology Group (ECOG) Performance Status, comorbidities, cancer stage, surgical procedures, types and doses of treatments, and other clinical characteristics. The study team will use the medical record to complete as much of this as possible. All other questionnaires will be completed by the participant, and all other measures will be obtained by the study team with the participant or the participants' blood samples.

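### The baseline-imbalance rule leaves the covariates of the 4-week FACIT-F model to be decided by the data, and the randomisation stratum is in no stated model

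*Combined protocol and SAP*

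**What the plan says.** Section 17.1 powers the trial on change in FACIT-F fatigue from baseline to 4 weeks, "using analysis of covariance (ANCOVA) with T1 FACIT-F as a covariate". Section 17.4.2 gives the same model, "with arm included as a fixed effect and FACIT-F fatigue score at baseline as a covariate".

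Section 17.2 plans a comparison of the arms at baseline: "Study arms will be compared on baseline demographic (e.g., age), clinical (e.g., cancer diagnosis, type of chemotherapy), and behavioral (e.g., physical activity, smoking) variables". The consequence follows: "If significant imbalance is found for a variable, it will be included as a covariate in subsequent analyses following standard practice". Five variables are named, each as an example. Section 8.2.2 shows what else the clinical record holds: "comorbidities, cancer stage, surgical procedures, types and doses of treatments, and other clinical characteristics".

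Two other sentences leave adjustment open. Section 4.4.4 says of factors associated with fatigue, depression being the example, "and we will adjust for these potential factors in our analyses". Section 17.4.2 adds age, gender and body mass index to see what they do to the results, which is best read as sensitivity work.

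Randomisation is stratified by planned chemotherapy frequency (Sections 4.3, 8.2.5 and 17.1). Section 4.3 gives the reason: to account for where in a cycle a patient is at weeks 4 and 8. No model in Sections 17.4.1 to 17.4.4 names the stratum.

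**The concern.** The imbalance rule is mandatory, comes before every analysis in Section 17.4, and is not overridden there. The covariates of the analysis that Section 17.1 calls primary are therefore unknown until the arms have been compared. The number of variables to be tested is not stated. Nor does the text say whether the section's general 0.15 level is meant for balance checks.

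The selection criterion is also the wrong one. With sound randomisation, a significant baseline difference is a chance event. A variable picked that way is correlated with arm by construction, so it widens the standard error of the arm effect unless it also predicts fatigue. The model run may have more terms than the model powered.

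Meanwhile the one factor that the protocol itself ties to the timing of fatigue is left out. Sections 2.1.1 and 8.2.7 say that fatigue moves with time since infusion, and Section 17.1 says that one stratum is assessed at the end of a cycle and the other in the middle. The imbalance rule is unlikely to bring the stratum in, because blocks of 3 or 6 within strata keep it balanced.

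At stake is pre-specification of the fatigue estimate, since Section 17.4.2 says the results "will be used in planning a future randomized trial".

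**Working it through.** **Inputs from Section 17.1:** 33 evaluable patients (22:11), standardised effect 0.75, baseline to 4-week correlation 0.50, two-sided level 0.15.

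**Assumed, because the documents do not say:** 5 or 10 variables tested, balance threshold 0.05 or 0.15, and covariates jointly explaining 0 to 30% of the variance left after baseline FACIT-F.

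**1. The plan's own figure.** Residual SD = √(1 − 0.50²) = 0.866. Standard error = 0.866 × √(1/22 + 1/11) = 0.866 × 0.369 = 0.320. Noncentrality = 0.75 / 0.320 = 2.35. Power is 81.7% by the normal approximation and 80.6% by noncentral t on 30 df. The stated 80% reproduces for arm plus baseline score. Simulation of the same model gives 79 to 80%.

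**2. How often something is flagged by chance.** For k independent variables at threshold a, the probability is 1 − (1 − a)^k.
- a = 0.15: 1 − 0.85⁵ = 56%; 1 − 0.85¹⁰ = 80%.
- a = 0.05: 1 − 0.95⁵ = 23%; 1 − 0.95¹⁰ = 40%.

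**3. Effect of the rule on power.** Trials were simulated from Y = 0.5 × baseline + 0.75 × arm + covariates + error, with variance 0.75 given baseline. Any covariate whose balance p-value fell below the threshold was added. There were 10,000 trials per scenario in the first row and 20,000 in the others. The first row takes the five named variables as age and activity continuous, smoking binary at 15%, cancer diagnosis at 3 or 5 levels and chemotherapy type at 3 or 4.

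| Variables screened | Threshold 0.15 | Threshold 0.05 |
|---|---|---|
| Five named, not prognostic | 79.5→75.9% and 79.3→74.9% | 79.3→77.3% and 79.7→77.6% |
| Ten independent, not prognostic | −5.6 points, to 73.7% | −3.2 points, to 76.8% |
| Independent, explaining 30% (5 / 10 variables) | −0.2 / −3.7 points | −0.5 / −1.8 points |
| Pairwise correlation 0.5, explaining 30% (5 / 10 variables) | +2.4 / +1.5 points | +1.4 / +1.1 points |

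**4. Changed conclusions.** Against the base model, with the five named variables at 0.15, 5.2 to 6.1% of trials lose significance and 1.7% gain it. At 0.05 the figures are 2.6% and 0.5 to 0.7%. With ten correlated prognostic variables at 0.15, 7.7% lose and 9.1% gain, so much of the disagreement there is useful adjustment.

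**5. Bias and type I error.** With five independent non-prognostic variables at 0.15, the mean estimate is 0.750 without the rule and 0.749 with it. Its SD rises from 0.3265 to 0.3431 (0.3431/0.3265 = 1.05). With ten, the SD goes from 0.324 to 0.359, about 11% more. Null rejection under the rule is 12.6 to 15.6% across the scenarios of steps 3 and 4, against a nominal 15%.

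**6. Adding the stratum.** Noncentral t on 29 df still gives 80.6%. Simulation used stratified blocks of 3 or 6, 33 of 42 patients retained at random, and 50% or 30% of patients in one stratum:

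| Residual variance explained by stratum | 50% in stratum | 30% in stratum |
|---|---|---|
| 0 | 79.6→79.2% | 79.3→78.8% |
| 10% | 80.3→82.2% | 80.4→82.7% |
| 20% | 81.3→85.9% | 80.7→85.6% |

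Under the null with 20% explained, rejection is 12.6% or 12.3% without the term and 15.4% or 15.0% with it. Leaving out a prognostic stratum makes the test conservative.

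**The case against.** Several points on the other side stand.

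- The rule does not bias the arm estimate, and the raw means and SDs that Section 17.4.2 also wants for planning are untouched by it.
- The first aim is feasibility. Its success criteria in Section 17.4.1 do not use this model, and no go/no-go decision depends on the fatigue test.
- The general 0.15 level in Section 17.2 is the natural default for the balance tests, so a threshold can be inferred.
- Section 8.2.2 lists what the record contains and does not say those items will be compared between arms. The ten-variable case is therefore an assumption; for the five named variables the loss is about 2 to 4 points.
- Some candidate covariates probably do predict fatigue, and the rule can then help.
- Section 8.2.7 aims for assessments at least 3 days after an infusion, which weakens the timing argument for the stratum, though Section 2.1.1 puts the fatigue peaks several days after infusion.
- Section 17.4.4 promises cautious reading of secondary and exploratory results. Whether that covers Aim 2 is unclear, because Section 17.1 calls the fatigue change primary.

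These points limit the size of the problem. They do not fix the covariate set in advance, and they give no reason to choose covariates by chance association with arm. If prognostic adjustment is wanted, naming the variables beforehand secures it.

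**Conclusion.** The concern holds, with minor to moderate consequences. As written, Section 17.2 can change the one model on which the sample size rests, and the stratum is missing from every stated model. The sample size calculation is correct for the model it describes, and there is no inflation of type I error.

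The effect of the rule on power runs from about −6 to +2 points and is often near zero. Where it falls depends on the number of variables, the threshold, their prognostic strength and their correlation, none of which the documents give. The gain from the stratum is also conditional: no stratum effect is documented, and the 10% and 20% shares are assumptions. The case for change is that the estimate carried into the next trial should come from a model known in advance, and that this costs almost nothing.

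**What to change.** Delete the imbalance sentence in Section 17.2 and state instead:

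*The primary model for FACIT-F fatigue at 4 weeks contains arm, baseline FACIT-F fatigue and the randomisation stratum (chemotherapy frequency), whatever baseline imbalance is observed. Baseline characteristics are described by arm without p-values.*

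Then:
- Name a short list of further covariates, chosen in advance for prognostic value, for one labelled sensitivity model. Point Sections 17.2, 17.4.2 and 4.4.4 to it.
- Note in Section 17.1 that the stratum term is added to the powered model.
- Say which covariates apply in the repeated-measures model and in the Section 17.4.3 and 17.4.4 analyses built on Aim 2, because deleting the sentence affects those too.

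The cost is wording in the combined protocol and SAP. A chance imbalance in another variable would be handled only in the sensitivity model. An inert stratum term costs under 1 point of power. The gain of 1 to 2 points that the rule would bring if the screened variables were correlated and strongly prognostic is given up in the primary model.
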